### 5.3 Flowchart of the study cohort assembly

	Optum		MarketScan		Medicare*	
	Less Excluded Patients	Remaining Patients	Less Excluded Patients	Remaining Patients	Less Excluded Patients	Remaining Patients
All patients		77,673,639		200,203,908		23,466,175
Did not meet cohort entry criteria	-73,445,846	4,227,793	-196,533,760	3,670,148	-18,348,713	5,117,462
Excluded due to insufficient enrollment	-623,954	3,603,839	-340,051	3,330,097	-1,288,867	3,828,595
Excluded due to prior use of referent	-3,168,921	434,918	-2,967,886	362,211	-3,495,789	332,806
Excluded due to prior use of exposure	-29,778	405,140	-12,511	349,700	-33,013	299,793
Excluded because patient qualified in >1 exposure category	-8	405,132	-3	349,697	-9	299,784
Excluded based on Age	0	405,132	-1	349,696	0	299,784
Excluded based on Gender	-39	405,093	0	349,696	0	299,784
Excluded based on Inclusion #1 - Age >=18 years old	-624	404,469	-1,354	348,342	-721	299,063
Inclusion #3 - HFpEF prediction algorithm applied to reference group†	-381,531	22,938	-337,242	11,100	-259,816	39,247
Excluded based on Inclusion #4b - Hospitalization for HF within the last 12 months	-9,321	13,617	-4,618	6,482	-10,685	28,562
Excluded based on Inclusion #5a - ACEis or ARBs	-1,224	12,393	-385	6,097	-1,534	27,028
Excluded based on Inclusion #5b - Beta-blockers	-673	11,720	-248	5,849	-2,128	24,900
Excluded based on Exclusion #3 - Known history of angioedema	-56	11,664	-29	5,820	-200	24,700
Excluded based on Exclusion #4 - Treatment with both ACEis AND ARBs	-15	11,649	-9	5,811	-34	24,666
Excluded based on Exclusion #5 - Acute decompensated HF	-1,060	10,589	-435	5,376	-5,457	19,209
Excluded based on Exclusion #6 - Symptomatic hypotension	-734	9,855	-240	5,136	-1,964	17,245
Excluded based on Exclusion #7 - Low eGFR / renal dysfunction	-1,064	8,791	-403	4,733	-2,833	14,412
Excluded based on Exclusion #8 - Hyperkalemia	-57	8,734	-14	4,719	-116	14,296
Excluded based on Exclusion #9 - ACS, Stroke, TIA, CABG, PCI, Other CV Procedures, Carotid Angioplasty	-765	7,969	-546	4,173	-2,912	11,384
Excluded based on Exclusion #11 - Implantation of CRT device	-41	7,928	-19	4,154	-1,550	9,834
Excluded based on Exclusion #12 - History of heart transplant or LVAD	-56	7,872	-33	4,121	-35	9,799
Excluded based on Exclusion #13 - History of severe pulmonary disease	-463	7,409	-205	3,916	-1,029	8,770
Excluded based on Exclusion #14 - Diagnosis of peripartum- or chemotherapy-induced cardiomyopathy	-38	7,371	-34	3,882	-60	8,710

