### 6.2 Preliminary Covariates:

- Age

- Sex
- Combined Comorbidity Index (CCI), measured over the default baseline covariate assessment period of 180 days prior to and including the index prescription date

Covariates listed above are a small subset of covariates that will ultimately be controlled in the design and analysis phase of the study. They are included in the preliminary assessment to determine the presence of adequate overlap between the two population of patients to proceed to the next phase of the study. Remaining covariates are defined only after the study has passed the initial feasibility analysis and initial power assessment and are listed in Table 1 (**Appendix B**).

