## 9. Balance Assessment

Optum- <https://bwh-dope.aetion.com/projects/details/1069/results/63131/result/0>

MarketScan- <https://bwh-dope.aetion.com/projects/details/1072/results/63129/result/0>

Medicare- <https://bwh-dope.aetion.com/projects/details/1073/results/63128/result/0>

Date conducted: 12/22/2020

After review of initial feasibility and power analyses, complete creation of the remaining covariates from Section 6.2. Again, using the

dummy outcome of a 90-day gap in database enrollment, complete a 1:1 PS-matched analysis. The PS should include the complete list of covariates.

- Provide plot of PS distributions stratified by treatment group.

Note- Please refer to **Appendix B**.

- Report covariate balance after matching.

Note- For Table 1, please refer to **Appendix B**.

- Report reasons for censoring by treatment group.

	Overall	Referent	Exposure
Dummy outcome	0 (0%)	0 (0%)	0 (0%)
Death	150 (2.47%)	64 (2.11%)	86 (2.84%)
Start of an additional exposure	309 (5.09%)	106 (3.49%)	203 (6.69%)
End of Index Exposure	2285 (37.67%)	1206 (39.76%)	1079 (35.58%)
Specified date reached	1868 (30.79)	879 (28.98%)	989 (32.61%)
End of patient enrollment	696 (11.47%)	366 (12.07%)	330 (10.88%)
Switch to ARBs or Aliskiren + Nursing Home admission Occurred	758 (12.50%)	412 (13.58%)	346 (11.41%)

- Report follow-up time by treatment group.

Patient Group	Optum Median Follow-Up Time (Days) [IQR]	MarketScan Median Follow-Up Time (Days) [IQR]	Medicare Median Follow-Up Time (Days) [IQR]
Overall Patient Population	118 [58, 286]	139 [59, 296]	102 [46, 189]
Referent - ACE Inhibitors	126 [60, 309]	142 [77, 295]	102 [42, 170]
Exposure - Sacubitril/Valsartan	108 [56, 266]	136 [58, 300]	106 [58, 218]

- Report overall risk of the primary outcome.

	Optum	MarketScan	Medicare	Pooled
Risk per 1,000 patients	206.6	160.3	248.0	215.3

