3	LVEF ≤ 35%	
Measured 180 days prior to and including the day of index drug initiation in any diagnosis position and inpatient or outpatient care setting
 
Systolic Heart Failure
 
ICD-9 diagnosis: 428.2x
 
ICD-10 diagnosis: I50.2x
 
Combined Systolic/Diastolic Heart Failure
 
ICD-9 diagnosis: 428.4x
 
ICD-10 diagnosis: I50.4x
		
4	Plasma BNP ≥150 pg/mL or NT-proBNP ≥600 pg/mL at the screening visit and a hospitalization for HF within the last 12 months			
4a	Plasma BNP ≥150 pg/mL or NT-proBNP ≥600 pg/mL at the screening visit			
AND the following:				

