# Appendix A

	Variable	Codes and Medications (all medical claims, inpatient and outpatient should be used to define the conditions unless otherwise specified)	Coefficients ("Score")	When Measured for replicating	When Measured ([name]'s algorithm)
1	Intercept	N/A	-1.37219		
2	Cardiomyopathy	ICD-9 diagnosis: 425.x ICD-10 diagnosis: I42.x, I43.x	1.415113	Measured 180 days prior to and including the date of index drug initiation	6 months prior to index date + index date + 30days post-index
3	Diastolic heart failure	ICD-9 diagnosis: 428.3x (not co-occurring with 428.2x ) ICD-10 diagnosis: I50.3x (not co-occurring with I50.2x)	-0.950856	Measured between 180 days prior to and including the date of drug initiation and pick claim closest to the index initiation	on index date
4	Left heart failure	ICD-9 diagnosis: 428.1x (not co-occurring with more specific systolic or diastolic HF codes of 428.2x or 428.3x) ICD-10 diagnosis: I50.1 (not co-occurring with more specific systolic or diastolic HF codes of I50.2x or I50.3x)	0.766415	Measured between 180 days prior to and including the date of drug initiation and pick claim closest to the index initiation	on index date
5	Systolic heart failure	ICD-9 diagnosis: 428.2x (not co-occurring with 428.3x) ICD-10 diagnosis: I50.2x (not co-occurring with I50.3x)	0.754954	Measured between 180 days prior to and including the date of drug initiation and pick claim closest to the index initiation	on index date
6	Myocardial infarction	ICD-9 diagnosis: 410.xx ICD-10 diagnosis: I21.01, I21.02, I21.09, I21.11, I21.19, I21.21, I21.29, I21.3, I21.4, I22.0, I22.1, I22.2, I22.8, I22.9	0.651778	Measured 180 days prior to and including the date of index drug initiation	6 months prior to index date + index date + 30days post-index
7	Unspecified heart failure	ICD-9 diagnosis: 428.0x, 428.4x, 428.9x, 428.2x PLUS 428.3x ICD-10 diagnosis: I50.4x, I50.8x, I50.9, I50.2x PLUS I50.3x	-0.577221	Measured between 180 days prior to and including the date of drug initiation and pick claim closest to the index initiation	on index date

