Calendar Time - Year of Initiation (2015/16 - 2020)	...2015-2016; n (%)	146 (11.4%)	153 (12.0%)	-0.0187	229 (30.6%)	233 (31.1%)	-0.0108	355 (35.3%)	374 (37.2%)	-0.0395	797 (26.3%)	785 (25.9%)	0.0091
...2017; n (%)	293 (22.9%)	280 (21.9%)	0.0240	264 (35.3%)	256 (34.2%)	0.0231	651 (64.7%)	632 (62.8%)	0.0395	293 (9.7%)	280 (9.2%)	0.0171	
...2018; n (%)	321 (25.1%)	319 (24.9%)	0.0046	255 (34.1%)	259 (34.6%)	-0.0105	0 (0.0%)	0 (0.0%)	#DIV/0!	321 (10.6%)	319 (10.5%)	0.0033	
...2019 - 2020; n (%)	519 (40.6%)	527 (41.2%)	-0.0122	0 (0.0%)	0 (0.0%)	#DIV/0!	0 (0.0%)	0 (0.0%)	#DIV/0!	519 (40.6%)	527 (41.2%)	-0.0122	
Combined comorbidity score, 180 days	...mean (sd)	5.30 (2.47)	5.27 (2.43)	0.0122	4.24 (2.12)	4.19 (2.06)	0.0239	4.77 (2.49)	4.76 (2.40)	0.0041	4.86 (2.40)	4.83 (2.33)	0.0127
...median [IQR]	5.00 [4.00, 7.00]	5.00 [3.00, 7.00]	0.0000	4.00 [3.00, 6.00]	4.00 [3.00, 5.00]	0.0000	4.00 [3.00, 6.00]	4.00 [3.00, 6.00]	0.0000	4.42 (2.40)	4.42 (2.33)	0.0000	
CV Comorbidity - Pulmonary hypertension/Other pulmonary heart disease; n (%)	250 (19.5%)	257 (20.1%)	-0.0151	132 (17.6%)	126 (16.8%)	0.0212	209 (20.8%)	223 (22.2%)	-0.0341	459 (15.1%)	480 (15.8%)	-0.0194	
CV Comorbidity - Other dysrhythmias; n (%)	735 (57.5%)	736 (57.5%)	0.0000	424 (56.7%)	409 (54.7%)	0.0403	506 (50.3%)	519 (51.6%)	-0.0260	1,241 (40.9%)	1,255 (41.4%)	-0.0102	
CV Comorbidity - Valve disorder; n (%)	254 (19.9%)	237 (18.5%)	0.0356	46 (6.1%)	49 (6.6%)	-0.0205	202 (20.1%)	203 (20.2%)	-0.0025	456 (15.0%)	440 (14.5%)	0.0141	
CV Comorbidity - Hospitalization for heart failure; n (%)	1,041 (81.4%)	1,051 (82.2%)	-0.0207	602 (80.5%)	593 (79.3%)	0.0299	743 (73.9%)	740 (73.6%)	0.0068	1,784 (58.8%)	1,791 (59.1%)	-0.0061	
CV Comorbidity - Implantable cardioverter defibrillator; n (%)	328 (25.6%)	303 (23.7%)	0.0441	170 (22.7%)	170 (22.7%)	0.0000	137 (13.6%)	145 (14.4%)	-0.0231	465 (15.3%)	448 (14.8%)	0.0140	
CV Comorbidity - Hypertension; n (%)	167 (13.1%)	169 (13.2%)	-0.0030	67 (9.0%)	73 (9.8%)	-0.0274	160 (15.9%)	150 (14.9%)	0.0277	327 (10.8%)	319 (10.5%)	0.0097	
CV Comorbidity - Hypertension; n (%)	1,206 (94.9%)	1,208 (94.4%)	-0.0043	666 (88.0%)	658 (88.0%)	0.0313	972 (96.6%)	960 (95.4%)	0.0613	2,178 (71.5%)	2,168 (71.5%)	0.0067	
CV Comorbidity - Coronary atherosclerosis and other forms of chronic ischemic heart disease; n (%)	959 (75.0%)	946 (74.0%)	0.0229	436 (58.3%)	427 (57.1%)	0.0243	780 (77.5%)	788 (78.2%)	-0.0193	1,739 (52.3%)	1,724 (52.2%)	0.0020	

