Other Comorbidity - COPD; n (%)	378 (29.6%)	380 (29.7%)	-0.0022	108 (14.4%)	104 (13.9%)	0.0143	290 (28.8%)	297 (29.5%)	-0.0154	668 (22.0%)	677 (22.3%)	-0.0072	
Other Comorbidity - Pneumonia; n (%)	263 (20.6%)	270 (21.1%)	-0.0123	147 (19.7%)	139 (18.6%)	0.0280	185 (18.4%)	203 (20.2%)	-0.0456	448 (14.8%)	473 (15.6%)	-0.0223	
Other Comorbidity - Acute kidney injury (AKI); n (%)	284 (22.2%)	321 (25.1%)	-0.0683	158 (21.1%)	150 (20.1%)	0.0247	259 (25.7%)	253 (25.1%)	0.0138	543 (17.9%)	574 (18.9%)	-0.0	

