...median (IQR)	15.93 [5.74, 32.88]	18.14 [6.52, 33.73]	-0.0600	10.53 [3.58, 20.38]	12.40 [5.11, 19.94]	-0.1150	16.10 [5.26, 32.03]	18.78 [5.57, 34.95]	-0.0796	14.65 (36.11)	16.94 (26.88)	-0.0719
SES Proxy - Low income indicator; n (%)	275 (21.5%)	299 (23.4%)	-0.0455	0 (0.0%)	0 (0.0%)	#DIV/0!	0 (0.0%)	0 (0.0%)	#DIV/0!	275 (9.1%)	299 (9.9%)	-0.0273
SES Proxy - Business type												
...Commercial; n (%)	325 (25.4%)	340 (26.6%)	-0.0274	0 (0.0%)	0 (0.0%)	#DIV/0!	0 (0.0%)	0 (0.0%)	#DIV/0!	325 (10.7%)	340 (11.2%)	-0.0160
...Medicare; n (%)	954 (74.6%)	939 (73.4%)	0.0274	0 (0.0%)	0 (0.0%)	#DIV/0!	0 (0.0%)	0 (0.0%)	#DIV/0!	954 (31.5%)	939 (31.0%)	0.0108
SES Proxy - Insurance Plan type												
...Comprehensive; n (%)	0 (0.0%)	0 (0.0%)	#DIV/0!	105 (14.0%)	94 (12.6%)	0.0412	0 (0.0%)	0 (0.0%)	#DIV/0!	105 (3.5%)	094 (3.1%)	0.0224
...HMO; n (%)	0 (0.0%)	0 (0.0%)	#DIV/0!	62 (8.3%)	71 (9.5%)	-0.0422	0 (0.0%)	0 (0.0%)	#DIV/0!	062 (2.0%)	071 (2.3%)	-0.0207
...PPD; n (%)	0 (0.0%)	0 (0.0%)	#DIV/0!	403 (53.9%)	400 (53.5%)	0.0080	0 (0.0%)	0 (0.0%)	#DIV/0!	403 (13.3%)	400 (13.2%)	0.0029
...Others; n (%)	0 (0.0%)	0 (0.0%)	#DIV/0!	178 (23.8%)	183 (24.5%)	-0.0164	0 (0.0%)	0 (0.0%)	#DIV/0!	178 (5.9%)	183 (6.0%)	-0.0042
SES Proxy - Dual status code (with Medicaid); n (%)	0 (0.0%)	0 (0.0%)	#DIV/0!	0 (0.0%)	0 (0.0%)	#DIV/0!	202 (20.1%)	203 (20.2%)	-0.0025	202 (6.7%)	203 (6.7%)	0.0000

\*Excluded from P5 model: Age Categories, Use of Lithium, Use of AGI & Meglitinides, PCSK9 Inhibitors, Use of heparin or LMWH, Hemodialysis/Peritoneal dialysis

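### No ejection-fraction phenotype variable (cardiomyopathy, heart-failure code type or predicted EF) is visible among the propensity-score covariates, so the balance checkpoint cannot see it

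*Protocol*

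**What the plan says.** Section 6.2 states that the covariates beyond age, sex and comorbidity index "are listed in Table 1 (Appendix B"). Section 9 then instructs: "The PS should include the complete list of covariates". The footnote to Appendix B removes a few items from the model (age categories, lithium, "Use of AGI & Meglitinides, PCSK9 Inhibitors, Use of heparin or LMWH, Hemodialysis/Peritoneal dialysis"). None of these describes heart-failure type.

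The cardiovascular comorbidity block of Appendix B has 17 rows, from pulmonary hypertension to CABG/PCI, in the same order before and after matching. The row for the heart failure itself is "CV Comorbidity - Hospitalization for heart failure; n" (%). ICD, CRT device, myocardial infarction (MI) and valve disorder are also listed. Mineralocorticoid antagonist (MRA), digoxin and loop diuretic appear under cardiovascular medication.

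EF is otherwise handled at cohort entry, and the protocol describes that in two ways:

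- **Appendix A, Inclusion #3** asks for a systolic code or a code for "Combined Systolic/Diastolic Heart Failure" in the 180 days up to index, with no arm restriction.
- **The Section 5.3 flowchart** has "Inclusion #3 - HFpEF prediction algorithm applied to reference group", with no cut-off stated.

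Appendix A also sets out the EF prediction algorithm with its coefficients. Its heart-failure code types are mutually exclusive; systolic heart failure, for example, is "428.2x (not co-occurring with 428.3x").

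**The concern.** Sacubitril/valsartan was tested in patients with reduced EF, and the protocol's inclusion criteria try to reproduce that population. EF phenotype plausibly influences both the choice of drug and the risk of heart-failure admission or death. A claims rule for entry still leaves a wide spread of phenotype among the patients it admits, so that spread has to be balanced between arms.

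The variables that the protocol itself treats as the best markers of EF are not visible in the PS list. Much weaker predictors are listed: atrial fibrillation has a coefficient of -0.002 and hyperlipidemia -0.002. Because the markers are not in the balance table either, the stop-and-review step after the Final Power Assessment could pass a cohort whose arms differ in EF phenotype.

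**Working it through.** **Weights (Appendix A algorithm).** Cardiomyopathy 1.415113. Code type: left 0.766415, systolic 0.754954, unspecified -0.577221, diastolic -0.950856. The combined codes 428.4x and I50.4x score as unspecified. The code types are levels of one variable, so two variables are missing. MI (0.651778) ranks among the largest coefficients and is in the table.

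**Spread among patients alike on listed covariates.** Assumed profile: man aged 70, one heart-failure admission, ACE inhibitor, beta-blocker, loop diuretic, hypertension, hyperlipidemia. Linear predictor before code type and cardiomyopathy:

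-1.37219 + 0.323651 + 0.346289 + 0.221748 + 0.087257 + 0.084251 - 0.098539 - 0.001805 - 70 × 0.005747 = -0.812

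Probability = 1/(1 + exp(-linear predictor)):

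| Code type nearest index | Cardiomyopathy | Predicted reduced EF |
|---|---|---|
| Combined/unspecified | no | 20.0% |
| Systolic | no | 48.6% |
| Combined/unspecified | yes | 50.7% |
| Systolic | yes | 79.6% |

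Both the systolic and the combined code satisfy the Appendix A version of Inclusion #3. The extremes differ on the logit scale by 0.754954 + 1.415113 + 0.577221 = 2.747, and exp(2.747) = 15.6.

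**How much the proxies absorb.** ICD, MRA and digoxin sum to 0.275032 + 0.166008 + 0.163224 = 0.604, against 1.415 for cardiomyopathy alone. If both patients have all three, the linear predictor before code type is -0.812 + 0.604 = -0.207 (unrounded inputs), and the extremes are still about 31% and 88%.

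**Possible effect on the hazard ratio.** No between-arm difference is reported, so the inputs are assumptions: prevalence of the phenotype differs by 10 to 20 points, its outcome hazard ratio H is 1.3 to 1.5, and baseline prevalence p is free. Approximate bias factor = [1 + (p + d)(H - 1)] / [1 + p(H - 1)].

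- Smallest corner, d = 0.10, H = 1.3, p = 0.90: 1.30/1.27 = 1.024.
- Largest corner, d = 0.20, H = 1.5, p = 0: 1.10/1.00 = 1.10.
- Same d and H with p = 0.80: 1.50/1.40 = 1.07.

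The range is therefore roughly 2% to 10%. At the upper end an HR of 0.80 would read 0.80 × 1.10 = 0.88 or 0.80/1.10 = 0.73, about the ends of the trial interval of 0.73 to 0.87.

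**Which entry screen produced the matched cohort?** Section 7 has 4,217 / 2,218 / 6,293 reference patients. Appendix B before matching has 17,244 / 10,721 / 18,303. The two do not agree, so eligibility cannot be relied on to have equalised EF.

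**Power baseline for the fix.** The pooled final figure reproduces: 6,066 × 0.21525 = 1,305.7 events, and Φ(√(1305.7/4) × |ln 0.8| - 1.96) = 0.981.

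**The case against.** **Absence is not proved.** In the copy available, rows are cut after "Other Comorbidity - Acute kidney injury (AKI); n" and before the diabetes-drug rows, and the footnote names items (AGI and meglitinides, dialysis) with no readable row. This stands as a limit on wording. It is weak as a rebuttal: the cuts fall in the Other Comorbidity and Other Medication blocks, whereas a heart-failure type row would belong in the cardiovascular block, which is continuous in both tables.

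**Proxies are listed and balanced.** This stands. For heart-failure hospitalization, ICD, CRT, MI, MRA, digoxin and loop diuretic, every database-level standardized difference after matching is at most 0.061 in absolute value. They reduce the concern, but balance on proxies does not establish balance on the phenotype.

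**A wider gap is tempting.** A diastolic code without cardiomyopathy gives 14.6% for the same profile, and against systolic plus cardiomyopathy the odds ratio is 22.7. A reader might infer that 15% and 80% patients are matched as equals. The documents do not support that as the general case. Appendix A's Inclusion #3 normally excludes a diastolic-only patient. Under the flowchart, any cut-off above 15% would remove such a patient from the reference arm. A patient with an earlier systolic and a later diastolic code could still enter, but the usual admissible low end is about 20%.

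**An odds ratio between two patients is not confounding.** Correct. Matching balances groups, and any omitted variable lets unlike patients be paired.

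**The score may be poorly calibrated here.** The protocol changes the algorithm's measurement windows, so the percentages illustrate the spread and are not estimates for this cohort.

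**Conclusion.** The point holds in a limited form. No EF-type variable is visible in the PS list, the protocol's own algorithm ranks these variables highest, and the checkpoint therefore cannot show whether the arms match on them. Under the code-based entry rule, patients alike on the listed covariates can run from about 20% to about 80% predicted reduced EF. Under the flowchart rule only the reference group is screened, so the arms may differ in phenotype by design.

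A reader might go further and conclude that the matched arms are confounded by EF. The documents do not show that: no between-arm figure is given, and the 2% to 10% shift rests entirely on assumed imbalance, assumed hazard ratio and unstated prevalence, with unknown direction. This should be fixed before outcomes are run; it does not demonstrate a biased result.

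**What to change.** 1. Reconcile the two versions of Inclusion #3 (Section 5.3 and Appendix A): state one rule, the arms it applies to, and the cut-off if the score is used. Reconcile the reference counts in Section 7 and Appendix B at the same time.
2. Before the outcome run, add to the PS, in both arms, an indicator for cardiomyopathy and indicators for the heart-failure code type nearest index. The code lists are already in Appendix A.
3. Re-match in each database. Add these rows to Table 1, with the predicted score computed without its ACE-inhibitor term, since that is the index drug in the reference arm. Review balance by database.
4. Restate the Final Power Assessment with the new number of pairs.

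**Cost.** One re-match and some loss of pairs. The loss may not be small if only the reference arm was screened on the score, because low-score exposed patients would then lack comparators. As an illustration on the protocol's own formula, losing an assumed 20% of pairs leaves 0.8 × 1,305.7 = 1,044.6 events and pooled power Φ(√(1044.6/4) × 0.2231 - 1.96) = 0.95. The single-database figures, already 0.73, 0.41 and 0.70, would fall further.

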# Appendix B: Sacubitril/Valsartan vs. ACE Inhibitors

Other Medication - DPP-4 Inhibitors ; n (%)	90 (7.0%)	85 (6.6%)	0.0159	56 (7.5%)	46 (6.1%)	0.0556	90 (8.9%)	85 (8.4%)	0.0178	180 (5.9%)	170 (5.6%)	0.0129
Other Medication - GLP-1 RA ; n (%)	51 (4.0%)	51 (4.0%)	0.0000	21 (2.8%)	23 (3.1%)	-0.0177	17 (1.7%)	13 (1.3%)	0.0329	068 (2.2%)	064 (2.1%)	0.0069
Other Medication - Metformin ; n (%)	337 (26.3%)	341 (26.7%)	-0.0091	179 (23.9%)	172 (23.0%)	0.0212	218 (21.7%)	217 (21.0%)	0.0024	555 (18.3%)	558 (18.4%)	-0.0206
Other Medication - NSAIDS (COX-2 Selective) ; n (%)	72 (5.6%)	64 (5.0%)	0.0268	36 (4.8%)	31 (4.1%)	0.0340	43 (4.3%)	43 (4.3%)	0.0000	115 (3.8%)	107 (3.5%)	0.0160
Other Medication - NSAIDS (Non-Selective) ; n (%)	126 (9.9%)	129 (10.1%)	-0.0067	136 (18.2%)	137 (18.3%)	-0.0026	35 (3.5%)	34 (3.4%)	0.0055	161 (5.3%)	163 (5.4%)	-0.0044
Other Medication - Use of antiplatelet agents ; n (%)	355 (27.8%)	377 (29.5%)	-0.0276	249 (32.2%)	237 (31.7%)	0.0242	282 (38.0%)	292 (39.0%)	-0.0232	637 (21.0%)	669 (22.1%)	-0.0268
Other Medication - Use of heparin and other low-molecular weight heparins ; n (%)*	29 (2.3%)	27 (2.1%)	0.0136	1 (0.1%)	0 (0.0%)	0.0447	27 (3.7%)	9 (0.9%)	0.1357	056 (1.8%)	036 (1.2%)	0.0494
Other Medication - Use of oral anti-coagulants ; n (%)	478 (37.4%)	470 (36.7%)	0.0145	255 (34.1%)	270 (36.1%)	-0.0419	429 (42.6%)	419 (41.7%)	0.0182	907 (29.9%)	889 (29.3%)	0.0131
Other Medication - Use of other hypertension drugs ; n (%)	149 (11.6%)	140 (10.9%)	0.0222	105 (14.0%)	97 (13.0%)	0.0293	105 (10.4%)	108 (10.7%)	-0.0098	254 (8.4%)	248 (8.2%)	0.0072
Other Medication - Use of antipsychotics ; n (%)	33 (2.6%)	36 (2.8%)	-0.0123	10 (1.3%)	11 (1.5%)	-0.0170	32 (3.2%)	27 (2.7%)	0.0296	065 (2.1%)	063 (2.1%)	0.0000
Other Medication - Use of dementia meds ; n (%)	35 (2.7%)	25 (2.0%)	0.0462	15 (2.0%)	14 (1.9%)	0.0072	33 (3.3%)	34 (3.4%)	-0.0056	068 (2.2%)	059 (1.9%)	0.0212
Other Medication - Use of antiparkinsonian meds ; n (%)	34 (2.7%)	38 (3.0%)	-0.0180	13 (1.7%)	13 (1.7%)	0.0000	26 (2.6%)	29 (2.9%)	-0.0183	060 (1.9%)	060 (1.9%)	-0.0139
Other Medication - Use of anxiolytics/hypnotics ; n (%)	78 (6.1%)	81 (6.3%)	-0.0093	39 (6.2%)	54 (7.2%)	-0.0830	54 (5.4%)	60 (6.2%)	0.0342	132 (4.6%)	143 (4.7%)	-0.0144
Other Medication - Use of anticoagulants ; n (%)	181 (14.2%)	194 (15.2%)	-0.0282	76 (10.2%)	68 (9.1%)	0.0373	165 (16.5%)	165 (16.4%)	0.0027	347 (11.4%)	359 (11.6%)	-0.0125
Other Medication - Use of antidepressants ; n (%)	306 (23.9%)	317 (24.8%)	-0.0210	159 (21.3%)	159 (21.3%)	0.0000	284 (28.2%)	280 (27.8%)	0.0089	590 (19.5%)	597 (19.7%)	-0.0050
Other Medication - Use of lithium ; n (%)*	0 (0.0%)	0 (0.0%)	#DIV/0!	3 (0.4%)	0 (0.0%)	0.0896	2 (0.2%)	0 (0.0%)	0.0633	002 (0.1%)	000 (0.0%)	0.0447
Other Medication - Use of Benzodiazepine; n (%)	397 (15.4%)	187 (14.6%)	0.0224	92 (12.3%)	104 (13.9%)	-0.0474	131 (13.0%)	141 (14.0%)	-0.0293	328 (10.8%)	328 (10.8%)	0.0000
Other Medication - Use of opioids ; n (%)	385 (30.1%)	386 (30.2%)	-0.0022	213 (28.5%)	206 (27.5%)	0.0223	267 (26.5%)	281 (27.9%)	-0.0315	652 (21.5%)	667 (22.0%)	-0.0121
Other Medication - Use of COPD/asthma meds ; n (%)	296 (23.1%)	269 (21.0%)	0.0507	139 (18.6%)	152 (20.3%)	-0.0430	195 (19.4%)	218 (21.7%)	-0.0569	491 (16.2%)	487 (16.1%)	0.0027
HU - Bone mineral density; n (%)	28 (2.2%)	28 (2.2%)	0.0000	8 (1.1%)	9 (1.2%)	-0.0094	16 (1.6%)	14 (1.4%)	0.0165	044 (1.5%)	042 (1.4%)	0.0084
HU - Flexible Sigmoidoscopy or colonoscopy or CT virtual colonoscopy; n (%)	61 (4.8%)	55 (4.3%)	0.0240	30 (4.0%)	27 (3.6%)	0.0209	36 (3.6%)	41 (4.1%)	-0.0260	097 (3.2%)	096 (3.2%)	0.0000
HU - Flu vaccine; n (%)	235 (18.4%)	238 (18.6%)	-0.0052	76 (10.2%)	83 (11.1%)	-0.0292	306 (30.4%)	304 (30.2%)	0.0044	541 (17.8%)	542 (17.9%)	-0.0262
HU - Mammogram; n (%)	63 (4.9%)	62 (4.8%)	0.0047	36 (4.8%)	30 (4.0%)	0.0390	51 (5.1%)	46 (4.6%)	0.0233	114 (3.8%)	108 (3.6%)	0.0106
HU - Frailty Score: Empirical Version 365 days												
...mean (sd)	0.22 (0.06)	0.22 (0.06)	0.0000	0.20 (0.05)	0.19 (0.05)	0.2000	0.24 (0.07)	0.24 (0.07)	0.0000	0.22 (0.06)	0.22 (0.06)	0.0000
...median (IQR)	0.21 [0.18, 0.25]	0.21 [0.18, 0.25]	0.0000	0.18 [0.16, 0.22]	0.18 [0.16, 0.21]	0.0000	0.22 [0.19, 0.27]	0.22 [0.19, 0.27]	0.0000	0.21 [0.16, 0.26]	0.21 [0.16, 0.26]	0.0000
HU - Number of hospitalizations during CAP												
...mean (sd)	1.06 (0.77)	1.08 (0.76)	-0.0261	0.98 (0.65)	0.95 (0.66)	0.0458	1.07 (0.91)	1.07 (0.90)	0.0000	1.04 (0.79)	1.04 (0.79)	0.0000
...median (IQR)	1.00 [1.00, 1.00]	1.00 [1.00, 1.00]	0.0000	1.00 [1.00, 1.00]	1.00 [1.00, 1.00]	0.0000	1.00 [1.00, 1.00]	1.00 [0.95, 1.00]	0.0000	1.00 [0.97, 1.00]	1.00 [0.97, 1.00]	0.0000
HU - Number of Emergency Department (ED) visits												
...mean (sd)	1.81 (2.51)	1.84 (2.32)	-0.0124	2.56 (5.33)	2.40 (3.90)	0.0343	1.73 (2.19)	1.65 (2.78)	0.0320	1.97 (3.35)	1.92 (2.93)	0.0159
...median (IQR)	1.00 [0.00, 3.00]	1.00 [0.00, 3.00]	0.0000	2.00 [0.00, 3.00]	2.00 [0.00, 3.00]	0.0000	1.00 [0.00, 3.00]	1.00 [0.00, 2.00]	0.0000	1.25 (3.35)	1.25 (2.93)	0.0000
HU - Number of Internal Medicine/Family Medicine Visits												
...mean (sd)	14.51 (18.56)	14.34 (19.30)	0.0090	9.77 (15.50)	8.91 (12.31)	0.0614	8.50 (9.54)	8.89 (10.84)	-0.0382	11.35 (15.32)	11.19 (15.28)	0.0105
...median (IQR)	9.00 [4.00, 18.00]	9.00 [4.00, 19.00]	0.0000	5.00 [2.00, 11.75]	5.00 [2.00, 11.00]	0.0000	6.00 [3.00, 11.00]	6.00 [3.00, 11.00]	0.0000	7.02 (15.32)	7.02 (15.28)	0.0000
HU - Number of Distinct Medication Prescriptions (not generalized to generics)												
...mean (sd)	33.63 (25.85)	33.96 (20.50)	-0.0141	30.49 (17.53)	30.50 (15.10)	-0.0006	31.27 (19.20)	32.09 (16.13)	-0.0462	32.07 (21.91)	32.49 (17.88)	-0.0210
...median (IQR)	30.00 [20.00, 43.00]	30.00 [20.00, 38.00]	-0.0857	28.00 [19.00, 38.00]	28.00 [20.00, 38.00]	0.0000	27.00 [19.00, 38.00]	29.00 [21.00, 40.00]	-0.1128	27.67 (21.91)	29.18 (17.88)	-0.0755
HU - Number of Cardiologist visits												
...mean (sd)	13.79 (13.06)	13.37 (10.66)	0.0352	6.17 (8.33)	6.95 (7.55)	-0.0981	11.33 (12.78)	11.70 (11.61)	-0.0303	11.09 (11.97)	11.23 (10.33)	-0.0125
...median (IQR)	11.00 [5.00, 18.00]	11.00 [6.00, 18.00]	0.0000	4.00 [0.00, 9.00]	5.00 [2.00, 10.00]	-0.1258	8.00 (3.00, 15.00)	9.00 (4.00, 15.00)	-0.0819	8.28 (11.97)	8.86 (10.33)	-0.0519
HU - Number of Electrocardiogram												
...mean (sd)	4.47 (4.88)	4.32 (4.33)	0.0325	3.27 (3.08)	3.22 (2.91)	0.0167	3.88 (3.82)	3.73 (3.96)	0.0386	3.98 (4.15)	3.85 (3.90)	0.0323
...median (IQR)	3.00 [1.00, 6.00]	3.00 [2.00, 6.00]	0.0000	2.00 [1.00, 4.00]	2.00 [1.00, 4.00]	0.0000	3.00 [1.00, 5.00]	3.00 [1.00, 5.00]	0.0000	2.75 (4.15)	2.75 (3.90)	0.0000
HU - Number of Echocardiogram												
...mean (sd)	2.86 (5.89)	2.82 (5.27)	0.0072	1.78 (2.00)	1.76 (1.58)	0.0111	1.66 (1.50)	1.62 (1.34)	0.0281	2.20 (4.05)	2.16 (3.60)	0.0104
...median (IQR)	1.00 [1.00, 3.00]	1.00 [1.00, 3.00]	0.0000	1.00 [1.00, 2.00]	1.00 [1.00, 2.00]	0.0000	1.00 [1.00, 2.00]	1.00 [1.00, 2.00]	0.0000	1.00 (4.05)	1.00 (3.60)	0.0000
SES Proxy - Copay for pharmacy cost (charges in U.S. \$)												
...mean (sd)	27.20 (42.97)	25.88 (29.41)	0.0359	14.87 (18.19)	14.75 (14.06)	0.0074	25.85 (36.56)	26.03 (30.53)	-0.0053	23.71 (36.11)	23.18 (26.88)	0.0167
...median (IQR)	15.93 [5.74, 32.88]	18.14 [6.52, 33.73]	-0.0600	10.53 [3.58, 20.38]	12.40 [5.11, 19.94]	-0.1150	16.10 [5.26, 32.03]	18.78 [5.57, 34.95]	-0.0796	14.65 (36.11)	16.94 (26.88)	-0.0719
SES Proxy - Low income indicator; n (%)	275 (21.5%)	299 (23.4%)	-0.0455	0 (0.0%)	0 (0.0%)	#DIV/0!	0 (0.0%)	0 (0.0%)	#DIV/0!	275 (9.1%)	299 (9.9%)	-0.0273
SES Proxy - Business type												
...Commercial; n (%)	325 (25.4%)	340 (26.6%)	-0.0274	0 (0.0%)	0 (0.0%)	#DIV/0!	0 (0.0%)	0 (0.0%)	#DIV/0!	325 (10.7%)	340 (11.2%)	-0.0160
...Medicare; n (%)	954 (74.6%)	939 (73.4%)	0.0274	0 (0.0%)	0 (0.0%)	#DIV/0!	0 (0.0%)	0 (0.0%)	#DIV/0!	954 (31.5%)	939 (31.0%)	0.0108
SES Proxy - Insurance Plan type												
...Comprehensive; n (%)	0 (0.0%)	0 (0.0%)	#DIV/0!	105 (14.0%)	94 (12.6%)	0.0412	0 (0.0%)	0 (0.0%)	#DIV/0!	105 (3.5%)	094 (3.1%)	0.0224
...HMO; n (%)	0 (0.0%)	0 (0.0%)	#DIV/0!	62 (8.3%)	71 (9.5%)	-0.0422	0 (0.0%)	0 (0.0%)	#DIV/0!	062 (2.0%)	071 (2.3%)	-0.0207
...PPD; n (%)	0 (0.0%)	0 (0.0%)	#DIV/0!	403 (53.9%)	400 (53.5%)	0.0080	0 (0.0%)	0 (0.0%)	#DIV/0!	403 (13.3%)	400 (13.2%)	0.0029
...Others; n (%)	0 (0.0%)	0 (0.0%)	#DIV/0!	178 (23.8%)	183 (24.5%)	-0.0164	0 (0.0%)	0 (0.0%)	#DIV/0!	178 (5.9%)	183 (6.0%)	-0.0042
SES Proxy - Dual status code (with Medicaid); n (%)	0 (0.0%)	0 (0.0%)	#DIV/0!	0 (0.0%)	0 (0.0%)	#DIV/0!	202 (20.1%)	203 (20.2%)	-0.0025	202 (6.7%)	203 (6.7%)	0.0000

\*Excluded from P5 model: Age Categories, Use of Lithium, Use of AGI & Meglitinides, PCSK9 Inhibitors, Use of heparin or LMWH, Hemodialysis/Peritoneal dialysis
